### 12.9.2 Local Tolerability Scale (LTS)

LTS scores will be summarized by treatment and visit for subject overall assessment (scores from 0=None to 4=Strong/Severe) and Investigator overall assessment (scores from 0=No irritation to 4=Very Severe) separately. LTS scores at the sensitive areas will be summarized by visit, area and treatment group for Investigator overall assessment, as well as listed by subject and anatomical site.

### 12.9.3 Clinical Laboratory Testing

All clinical laboratory (hematology, clinical chemistry, urinalysis) values will be listed by subject. The reference normal ranges and reference range indicators (e.g. high, low, normal etc.) will be supplied by the central laboratory and displayed in the data listings. For the purpose of shift table summaries, the central lab reported reference range indicators will be classified as low, normal and high accordingly based on the table below. Change from baseline in abnormality status will be summarized using shift tables. For urinalysis, only lab tests with numeric results reported are included in shift tables. Separate listings will identify subjects with markedly abnormal values. For quantitative measures, observed values and changes in clinical laboratory values will be summarized descriptively by visit and treatment group.

Reference Range Indicator in Shift Tables	Reference Range Indicator Reported by Central Lab	
Low	Low, Low Level 1 Alert, Low Lever 2 Alert	
Normal	Normal	
High	High, High Level 1 Alert, High Level 2 Alert	

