### 1.3.1.2. Systemic Adverse Events

Nasopharyngitis and headache were the most frequently-reported nondermatological AEs in dose-ranging Study 203120 in psoriasis. In dose-ranging Study 203121 in AD, the most frequently reported nondermatological AEs were nasopharyngitis, upper respiratory tract infection, and headache. In the initial clinical studies (in AD and psoriasis) using a different tapinarof formulation (Formulation C), nasopharyngitis, and headache were the most frequently reported nondermatological AEs. In the open-label PK Study 201851 with BID dosing of Formulation F of tapinarof cream (n=11), 1% and 2%, headache was the most frequently reported during the study (reported for 100% and 60% of subjects at the 1% and 2% doses, respectively).

In a nonclinical study in minipigs using intravenous (IV) administration, reversible decreases in arterial blood pressure and PR interval were observed; however, in this study and repeat dermal toxicity studies, there were no effects on QT interval or heart rate. Repeat-dose dermal toxicity studies also showed findings related to the liver (increased weights and hepatocellular hypertrophy/regeneration) and thymus (thymic cortex depletion in adult rabbits and rats; changes in thymus weight, microscopic decreased cellularity, and changes in thymic T cell maturation in juvenile rats) with associated secondary hematological findings. Thymic findings were also noted in repeat adult and juvenile rat studies; however, there were no clinically relevant AEs/serious adverse events (SAEs) reported.

To mitigate potential systemic risks, subjects will be monitored for AEs and any abnormal vital signs, physical examination, and laboratory test results.

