## 4.3. Exclusion Criteria

A subject who meets any of the following criteria will be excluded and considered ineligible for participation in the study:

- 1. Psoriasis other than plaque variant
- 2. Any sign of infection of any of the psoriatic lesions
- 3. Concurrent conditions or history of other diseases:
- a. Immunocompromised (eg, lymphoma, acquired immunodeficiency syndrome) or medical history of positive human immunodeficiency virus (HIV) antibody at Screening
- b. Chronic or acute systemic infection requiring treatment with systemic antibiotics, antivirals, antiparasitics, antiprotozoals, or antifungals within 4 weeks prior to the Baseline visit
- c. Acute active bacterial, fungal, or viral (herpes simplex, herpes zoster, chicken pox) skin infection within 1 week prior to the Baseline visit
- d. Significant dermatologic or inflammatory condition other than plaque psoriasis that, in the Investigator's opinion, would make it difficult to interpret data or assessments during the study
- 4. Screening alanine aminotransferase (ALT) or aspartate aminotransferase (AST)  $\geq$  1.5x the upper limit of normal (ULN)
- 5. Screening total bilirubin > 1.5 x ULN; total bilirubin > ULN and  $\leq 1.5$  x ULN is acceptable if bilirubin is fractionated and direct bilirubin  $\leq 35\%$ .
- 6. Corrected QT (QTcF) interval > 475 msec.
- 7. Current or chronic history of liver disease, known hepatic or biliary abnormalities (with the exception of Gilbert's syndrome or asymptomatic gallstones), presence of hepatitis B surface antigen (HBsAg), or positive hepatitis C antibody test result, or a positive antihepatitis B core antigen (anti-HBc) result. Subjects with a history of HCV infection who were medically cured and have an undetectable viral load are eligible to enroll. Subjects with a history of stable non-alcoholic fatty liver disease without evidence of active inflammation (elevated ALT/AST ≥ 1.5x ULN) or cirrhosis are eligible to enroll.
- 8. Ultraviolet (UV) light therapy or prolonged exposure to natural or artificial sources of UV radiation (eg, phototherapy, tanning beds/booths, or therapeutic sunbathing) within

- 4 weeks prior to the Baseline visit and/or plans to have such exposures during the study which could potentially impact the subject's psoriasis (as determined by the Investigator).

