### 11.3 Baseline and Change from Baseline

Baseline value is defined as the last non-missing value prior to the first dose of study drug. Change from baseline is defined as the post-baseline value minus the baseline value unless otherwise specified. Percent change from baseline is calculated as follows: Percent change = (Change from baseline / Baseline) \* 100.

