### 12.9 Safety Analysis

All safety analyses will be conducted in the Safety Population. Data will be listed by subject and treatment and summarized by treatment. No formal statistical comparisons will be made for safety data.

Single 12-lead ECGs, Hospital Anxiety and Depression Scale (HADS) collected at Screening visit will be presented in a by-subject listing.

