### 12.9.4 Vital Signs

Observed values and changes in vital sign parameters (systolic and diastolic blood pressure [SBP, DBP], pulse rate, and body temperature) will be summarized descriptively by visit and treatment group. Vital sign values will be classified as normal, low, high, based on reference ranges as per Table below. Subjects with markedly abnormal changes will be listed and tabulated separately.

	Absolute Values			Change (Absolute) from Baseline	
	Low	Normal	High	Abnormal Change	Markedly Abnormal Change
SBP	<90 mmHg	90-140 mmHg	>140 mmHg	≥ 20 mmHg	≥ 40 mmHg
DBP	<50 mmHg	50-90 mmHg	>90 mmHg	≥ 10 mmHg	≥ 20 mmHg
Pulse	<50 bpm	50-100 bpm	>100 bpm	≥ 10 bpm	≥ 30 bpm

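### SAP 12.9.3 and 12.9.4 give no by-arm count of subjects by laboratory alert level or by direction of blood-pressure change

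*SAP*

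**What the plan says.** **Laboratory.** SAP 12.9.3 states that, for the shift tables, "the central lab reported reference range indicators will be classified as low, normal and high accordingly". The mapping table sends three central-laboratory indicators, "High, High Level 1 Alert, High Level 2 Alert", to the single class High, and does the same on the low side. The same section displays the indicators in the listings, lists subjects with markedly abnormal values (no threshold given), and summarizes observed values and changes by visit and treatment group.

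**Vital signs.** SAP 12.9.4 classes values as Low, Normal or High. Its change columns, headed as absolute change, use at least 20 and at least 40 mmHg for SBP and at least 10 and at least 20 mmHg for DBP, with no sign. It then says: "Subjects with markedly abnormal changes will be listed and tabulated separately". SAP 11.3 gives the general rule: "Change from baseline is defined as the post-baseline value minus the baseline value", unless otherwise specified.

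**Context.** Protocol 1.3.1.2 reports that "reversible decreases in arterial blood pressure and PR interval were observed" in minipigs given the drug intravenously. It also describes liver findings in repeat-dose dermal studies, along with thymic findings and secondary hematological findings. Protocol 4.3 excludes ALT or AST only from 1.5 x ULN upward, and admits stable fatty liver disease below that limit. Protocol section 2 makes clinically significant change in laboratory values and in vital signs safety endpoints. SAP 12.9 says "No formal statistical comparisons will be made for safety data".

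**The concern.** With no formal safety comparisons and no independent data monitoring committee (Protocol 8.6), descriptive tables by arm carry the safety comparison. A three-class shift table cannot register worsening in a subject who starts above the upper limit, and it gives every rise from Normal the same weight. A change table without direction cannot separate falls from rises, although a fall is the direction reported in Protocol 1.3.1.2. At stake is whether the study report can state, for each arm, how many subjects reached an alert level and how many had a large fall in blood pressure.

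**Working it through.** The plan states no figure to reproduce here. The check applies the SAP's own coding rules to example values and then adds an illustration on stated assumptions.

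**1. Laboratory shift coding**

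Inputs:
- The three-class mapping (SAP 12.9.3).
- The ALT/AST limit of 1.5 x ULN (Protocol 4.3).
- Baseline as the last value before first dose (SAP 11.3). Laboratory tests are not scheduled on Day 1 (Protocol Table 1), so the screening value will normally serve.

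Rule: High if the value exceeds ULN, whatever the alert level. The values below are examples, in multiples of ULN.

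| Baseline | Post-baseline | Shift shown |
|---|---|---|
| 1.4 | 0.9 | High to Normal |
| 1.4 | 1.3 | High to High |
| 1.4 | 3.5 | High to High |
| 1.4 | 9 | High to High |
| 0.8 | 1.1 | Normal to High |
| 0.8 | 3.5 | Normal to High |
| 0.8 | 9 | Normal to High |

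From a High baseline the table offers no worsening step. With the three supplied indicators kept apart it would offer two (High to Level 1, High to Level 2). From a Normal baseline there would be three upper destinations instead of one. The alert limits are not in the documents, so the multiple of ULN at which a step would appear is unknown.

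**2. Blood-pressure flags on single subjects**

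- SBP 130 to 92: 92 - 130 = -38. The value 92 lies within 90-140, so it is Normal. The change is short of 40, so it is not marked. It meets the 20 mmHg column, but 12.9.4 states no output for that column.
- SBP 150 to 110: a fall of 40. Read as magnitude, it gets the same marked flag as a rise of 40. Read as signed change, it gets none.
- SBP 105 to 88: classed Low, so visible there.

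**3. What pooling does to an arm comparison**

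Assumptions: change is normally distributed; the true mean change is -5 mmHg in one arm and 0 in the other; SD is 8 to 14 mmHg. None of these is in the documents.

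Fall rate = Φ((-20 - μ)/SD). Rise rate = 1 - Φ((20 - μ)/SD).

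For SD 14 and μ = -5: Φ(-15/14) = 14.20% falls and 1 - Φ(25/14) = 3.71% rises, 17.91% together. For μ = 0: 7.66% each way, 15.31% together (before rounding).

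| SD | Flag at 20 mmHg | μ = -5 | μ = 0 | Ratio | Difference (points) |
|---|---|---|---|---|---|
| 8 | pooled | 3.13% | 1.24% | 2.5 | 1.9 |
| 8 | falls only | 3.04% | 0.62% | 4.9 | 2.4 |
| 8 | rises only | 0.09% | 0.62% | 0.15 | -0.5 |
| 14 | pooled | 17.91% | 15.31% | 1.2 | 2.6 |
| 14 | falls only | 14.20% | 7.66% | 1.9 | 6.5 |
| 14 | rises only | 3.71% | 7.66% | 0.5 | -4.0 |

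A 20 mmHg cut-off is the abnormal column for SBP and the marked column for DBP. At the marked SBP cut-off of 40 mmHg and SD 14, pooled rates are 0.69% v 0.43% and falls alone 0.62% v 0.21%. With about 333 subjects, 0.62% is about 2 people (0.0062 x 333 = 2.1), so those cells would be sparse.

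**The case against.** The strongest reply is that much of the information is reported elsewhere.

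- By-arm summaries of values and changes include minimum and maximum (SAP 11.1, 12.9.3, 12.9.4). An ALT of 9 x ULN would drive an arm's maximum, and a large fall its minimum change. Mean change in blood pressure is signed.
- Listings carry the alert indicators.
- Protocol 8.1.1 makes abnormal results judged clinically significant adverse events, and SAP 12.9.1 tabulates TEAEs by maximum CTCAE grade.
- The Low class catches SBP below 90 and DBP below 50.
- The rises-only reading is strained, because the SAP 11.3 definition yields where otherwise specified and the 12.9.4 header calls the change absolute. On the magnitude reading a fall from 150 to 105 (45 mmHg) is flagged, and the listing shows its direction.
- If rises are equally common in both arms, pooling leaves the absolute difference unchanged: with assumed falls of 3% v 1% and rises of 3% in each arm, 6% - 4% = 3% - 1% = 2 points.

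Most of this stands, and it rules out stronger readings. A reader might infer that the plan conceals a liver or hypotensive signal; it does not. A reader might infer that a subject who starts High can only show no shift; improvement to Normal is possible. A reader might take liver and blood pressure to be the only systemic findings in Protocol 1.3.1.2. That section also names PR interval, thymus with hematological findings, and common events such as headache, and the blood-pressure finding was reversible and came from intravenous dosing in minipigs.

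What the reply does not supply is a count. Extremes by visit do not say how many subjects reached an alert level. Listings are not counts by arm, and 2:1 allocation makes them hard to compare by eye. The adverse-event route depends on the investigator judging a result clinically significant. The equal-difference argument fails when the whole distribution shifts, because rises then become rarer in the arm with the fall: at SD 14 the difference shrinks from 6.5 to 2.6 points.

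**Conclusion.** The point holds as a minor gap in tabulation. That the shift table cannot show worsening from a High baseline follows from the SAP's mapping and needs no assumption. That falls are not tabulated separately holds under either reading of the change column, as far as the SAP text goes; table shells are not among the documents. The practical size is unknown: the documents do not give the number enrolled with ALT or AST above ULN, the alert limits (or whether they apply to each analyte), or the spread of blood-pressure change. The percentages above are illustrations only. No efficacy conclusion or error rate is affected, and nothing contradicts the protocol, which asks for shift tables only where applicable. Label: cheap improvement.

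**What to change.** **SAP 12.9.3:** keep the central-laboratory levels (Low with its two alert levels, Normal, High with its two alert levels) as separate shift rows and columns, at least for ALT, AST and total bilirubin. Add a baseline-to-worst-post-baseline shift for those three. State the criterion behind the markedly abnormal listing.

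**SAP 12.9.4:** at the existing cut-offs, tabulate abnormal and markedly abnormal increases and decreases separately by arm. This also settles how the word absolute in the column header is to be read.

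The cost is SAP wording and table shells, using values and indicators already supplied. The downside is larger tables with sparse cells, especially at the marked SBP cut-off. Study conduct does not change.

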### 12.9.4 Vital Signs

Observed values and changes in vital sign parameters (systolic and diastolic blood pressure [SBP, DBP], pulse rate, and body temperature) will be summarized descriptively by visit and treatment group. Vital sign values will be classified as normal, low, high, based on reference ranges as per Table below. Subjects with markedly abnormal changes will be listed and tabulated separately.

	Absolute Values			Change (Absolute) from Baseline	
	Low	Normal	High	Abnormal Change	Markedly Abnormal Change
SBP	<90 mmHg	90-140 mmHg	>140 mmHg	≥ 20 mmHg	≥ 40 mmHg
DBP	<50 mmHg	50-90 mmHg	>90 mmHg	≥ 10 mmHg	≥ 20 mmHg
Pulse	<50 bpm	50-100 bpm	>100 bpm	≥ 10 bpm	≥ 30 bpm

### 12.9.5 Physical Examination

Brief physical examination results including weight, height, and BMI will be listed.

### 12.10 Pharmacokinetic Analyses

Plasma concentration data at Weeks 4 and 12 will be listed and summarized for the tapinar of cream, 1% group. Listings will be sorted by treatment, subject, day, and time.

The plasma concentrations divided by baseline total %BSA affected in  $cm^2$  will be summarized descriptively as well. For this calculation, 1% BSA is equal to 185  $cm^2$ .

Descriptive summaries will include n, mean, SD, median, minimum, and maximum. Concentration values below the limit of quantification will be treated as 0 in the summary.

In addition, plasma concentration at Weeks 4 and 12 will be summarized for the following subgroups:

- Age (<65 and >= 65 years old)
- Sex
- Race (White, Other)

Exploratory analyses may include relationships of plasma concentrations with patient demographics or AEs.

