<sup>k Photography will be performed in a subgroup of subjects at selected (8 to 10) study centers; this is not required of subjects for participation in the study. Informed consent/assent and photographic release will be required.

Blood sample collection for PK will be performed at a subset of sites in a subset of subjects. Sample to be collected prior to study drug application in clinic.

<sup>m The PGA assessment should be performed before the %BSA and PASI assessments.

<sup>n The subject's scalp, palms, fingernails toenails, and soles should be excluded from the %BSA calculations.

O %BSA affected calculation should be completed before the PASI assessment. Note that lesions on scalp, palms, fingernails, toenails, and soles will not be included in the calculation of %BSA affected as these areas will be excluded from the efficacy analyses.

<sup>p The LTS assessment also consists of a subject-assessed component (Section 6.3.5).

 $^{\rm q}$  Subjects should perform the Peak Pruritus NRS assessment daily (Section 6.2.2.4) and record the results in their diary. On study visit days, subjects will not complete the diary at home; application time and NRS will be recorded in the clinic.

<sup>r Subjects will be instructed on when and how to complete diaries.

Subjects will be instructed to apply study drug once daily at the approximate same time each day, based on subject preference (Section 5.1.5).

<sup>t At clinic visits, study drug will be applied after safety and efficacy assessments have been conducted (see Section 5.1.5 for additional details on timing of application of study drug during clinic visits).

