## 5.1.5. Administration of Study Drug

Study drug will be dispensed to subjects at the clinical site in appropriately labeled tubes.

Subjects will take the tubes home and self-administer study drug (or have caregiver apply if necessary), except on clinic visit days (when study drug is applied under supervision at the site), to affected areas once daily.

Subjects will be instructed to apply study drug as follows:

- Once daily application to affected areas; subjects are to choose the application time they prefer and to apply the study drug at that approximate time each day of study participation.
- If a subject misses a daily dose, it will be recorded as a protocol deviation. The subject should continue dosing the next day and should not apply more than once daily to make up for the missed dose on the previous day.
- If chosen application time is in the evening, the dose should be applied at least 30 minutes prior to bedtime.
- Study drug should be applied to dry, clean skin.
- Wash hands after application, unless treating lesions on the hands or fingernails.
- Study drug should be applied to all lesions, including newly appearing lesions and lesions that have improved during the study.
- Subjects are allowed, but not required, to treat fingernails, toenails, palms, soles, and scalp lesions with study drug; however, efficacy analyses will not include assessment of improvement of psoriasis in these areas. If using study drug on the scalp, no other treatment for scalp psoriasis is permitted during the study.
- If there is residual cream visible on the disease-affected lesional skin, then the subject should be instructed to continue to lightly rub the cream into the skin until it is no longer visible.
- If study drug is applied to the subject by another person, that person should thoroughly wash his/her hands after application. When possible, use of disposable gloves is recommended.
- Subjects should record the time of study drug application in the daily diary.
- Subjects should avoid swimming, bathing, showering, or strenuous activities for at least 2 hours after application of study drug.
- On clinic visit days, study drug should be applied in the clinic under the supervision
  of site personnel and after safety and efficacy assessments have been completed
  NOTE: The time of the dose and assessments on clinic visit days will depend on the
  time of the clinic visit. Therefore, the timing of the clinic visit may differ from the

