#### 6.5. Pharmacokinetics

A single blood sample for PK analysis of tapinar of cream, 1% will be collected at a subset of sites in a subset of subjects at timepoints indicated in the Schedule of Assessments (Table 1) and Section 7. The actual date and time of each blood sample collection will be recorded as well as the date and time of the last dose of study drug prior to sample collection. Collection, processing, storage, and shipping procedures are provided in the Laboratory Manual.

Concentrations of tapinarof will be determined in plasma samples using a validated bioanalytical method. Raw data will be archived at the bioanalytical site.

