#### 10.4.5. Pharmacokinetic Analyses

Data will be listed and summarized. Listings will be sorted by subject, day, and time; summaries will be presented by study visit and time from last dose.

Unless stated otherwise, descriptive summaries for continuous variables will include n, mean, SD, median, minimum, and maximum. If data permit, time to steady state will be assessed using the sampled trough values. Exploratory analyses may include relationships of plasma concentrations with patient demographics or AEs.

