### 13. CHANGES FROM THE PROTOCOL AND PLANNED ANALYSES

The protocol specified change over time in physical component score and mental component score as measured by the SF-36 questionnaire as an exploratory endpoint. Scoring rules for the RAND 36-Item Health Survey (Version 1.0) are provided for the eight domain scores but not for the physical component score or the mental component score. Hence, summaries of the eight domain scores are planned.

No other changes from the protocol in planned analyses are noted. Any additional statistical analyses to handle modifications to study conduct and/or missing data due to the COVID-19 pandemic have been documented in Section 12.11 above in this SAP and will be finalized prior to database lock and unblinding of the study.

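### SAP 12.10 leaves out the time-from-last-dose PK summary and the steady-state assessment planned in protocol 10.4.5, and SAP 13 declares neither omission

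*SAP*

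**What the plan says.** Protocol 10.4.5 sets two axes for the plasma concentration tables: "summaries will be presented by study visit and time from last dose". It also plans, if the data permit, an assessment of time to steady state from trough samples. Protocol 6.5 collects what is needed for the second axis: the sampling time is recorded "as well as the date and time of the last dose of study drug prior to sample collection".

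SAP 12.10 begins: "Plasma concentration data at Weeks 4 and 12 will be listed and summarized for the" tapinarof group. It continues "Listings will be sorted by treatment, subject, day, and time", and then "In addition, plasma concentration at Weeks 4 and 12 will be summarized for the following subgroups", namely age, sex and race. It also plans concentrations divided by baseline affected BSA, and sets values below the limit of quantification to 0. It contains no summary by time from last dose and no steady-state assessment.

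After describing the SF-36 change, SAP 13 states: "No other changes from the protocol in planned analyses are noted", apart from the COVID-19 analyses.

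The protocol synopsis, under Pharmacokinetic Analyses, plans summaries by study visit and names no second axis.

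**The concern.** Characterising the PK of tapinarof is a stated secondary objective, and each PK subject gives a single sample per PK visit. A single concentration can be read only together with the time since the last application. The protocol recognises this in 6.5 and 10.4.5. The SAP does not carry it through, although it adds subgroup tables whose reading depends on it.

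If concentrations fall appreciably over the dosing interval, the pooled mean at a visit depends partly on how many subjects were sampled early or late in that interval. A difference between subgroups could then reflect sampling time rather than exposure. The pooled tables cannot show whether this has happened.

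There is also a traceability problem. A reader of SAP 13 would conclude that the PK analysis follows the protocol, and in two respects it does not.

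**Working it through.** **1. The PK plans side by side**

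| Item | Protocol synopsis | Protocol 10.4.5 | SAP 12.10 |
|---|---|---|---|
| Summary by visit | yes | yes | yes (Weeks 4, 12) |
| Summary by time from last dose | not mentioned | yes | no |
| Time to steady state | not mentioned | if data permit | no |
| Age, sex, race; divided by BSA | not mentioned | not listed as summaries | yes |
| Declared in SAP 13 | – | – | no |

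The SAP revision history records three PK changes for Version 3.0: the BSA-adjusted summary, the subgroup summaries and removal of the geometric mean. None concerns time from last dose or steady state.

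**2. Why the interval varies**

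- The note to protocol Table 1 says: "Sample to be collected prior to study drug application in clinic". The last application before sampling is therefore normally the previous day's home application.
- Under protocol 5.1.5, "subjects are to choose the application time they prefer", and evening use is allowed.
- Protocol 3.1 and 5.1.5 both accept that the clinic visit may not match the chosen time.
- No document fixes a clock time or a number of hours after application for the sample.

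**3. Size of the variation (clock times assumed; the documents give none)**

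Hours since last dose = visit time + 24 − previous day's dose time.

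| Dose | Visit | Hours |
|---|---|---|
| 22:00 | 08:00 | 8 + 24 − 22 = 10 |
| 21:00 | 09:00 | 9 + 24 − 21 = 12 |
| 08:00 | 09:00 | 9 + 24 − 8 = 25 |
| 07:00 | 16:00 | 16 + 24 − 7 = 33 |

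With doses at 07:00-22:00 and visits at 08:00-16:00, the range is 10 to 33 h. A missed application on the previous day would add 24 h.

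Under these times, a sample taken before the in-clinic application is not always an end-of-interval sample. An evening user seen next morning is sampled about halfway through a 24 h interval, so the protocol's word trough fits only some of the samples.

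**4. What this could mean for concentration (half-lives assumed; none is given)**

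Under simple first-order decline, the ratio of a 12 h to a 25 h concentration in the same subject is 2^((25 − 12)/half-life) = 2^(13/half-life):

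| Assumed half-life | Ratio |
|---|---|
| 4 h | 2^(13/4) = 9.5 |
| 8 h | 2^(13/8) = 3.1 |
| 12 h | 2^(13/12) = 2.1 |
| 24 h | 2^(13/24) = 1.5 |
| 48 h | 2^(13/48) = 1.2 |

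If continuing absorption from skin keeps levels flat, the ratio approaches 1. If both samples are below the limit of quantification and set to 0, the ratio does not apply. The documents do not say which case holds.

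**5. Steady state**

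PK samples are taken at Weeks 4 and 12 only. Two visits, the first after four weeks of daily application, are very unlikely to support an estimate of time to steady state.

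**The case against.** The SAP agrees with the synopsis and with the protocol's only PK endpoint, plasma concentration at Weeks 4 and 12; the conflict is with 10.4.5. That stands, and it means the synopsis needs aligning as well.

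SAP section 1 says the plan will not repeat every protocol definition. That does not cover this case. A summary axis is an analysis rather than a definition, and 12.10 gives its own list of summaries, carrying over the protocol's listing order but not the summary rule beside it.

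The steady-state assessment was conditional on the data. That also stands: leaving it out is reasonable, and the gap is that it is not declared.

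A reader might infer several stronger things that the documents do not support:

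- **That the SAP summarises by visit and nothing else.** It also summarises by age, sex and race and divides by affected BSA. What is missing is the time axis.
- **That samples are known to fall at about 12 h and 25 h.** These are examples from assumed clock times.
- **That Week 12 is less controlled because no supervised application is scheduled then.** The Week 4 sample also precedes the in-clinic application, so supervision fixes the interval at neither visit.
- **That Week 4 against Week 12 is badly confounded by choice of application time.** Subjects are told to keep roughly the same time throughout, so the mix should be similar at both visits among those sampled twice. Variation in clinic time and dropout remain. The SAP plans no test between the two visits.
- **That subgroups differ in application time.** Nothing in the documents says so; it is only a possibility the pooled tables could not exclude.

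**Conclusion.** The point holds as an undeclared inconsistency between protocol 10.4.5 and SAP 12.10, with a modest consequence for interpretation. The two omissions, and their absence from SAP 13, follow from the text and need no assumption. That time since last application will vary between subjects follows from the sampling and application rules. The 10 to 33 h range rests on assumed clock times.

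The effect on the PK summaries cannot be sized. The illustrative ratios run from close to 1 up to 9.5, depending entirely on an assumed half-life and form of decline, so they do not show that the pooled tables will mislead. They show only that those tables could not reveal it if they did.

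The impact is confined to a descriptive secondary objective. The primary and secondary efficacy analyses, alpha control and power are untouched. This is a cheap improvement, not a threat to the trial's conclusions.

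**What to change.** 1. **SAP 12.10:** restore the summary of Week 4 and Week 12 concentrations by time from last dose, in bands set before any concentrations are seen (for illustration: up to 16 h, over 16 to 28 h, over 28 h). Add a plot of concentration against time from last dose, by visit. Keep the all-sample tables, including the subgroup and BSA-adjusted ones. Do not confine visit or subgroup summaries to one band: 10.4.5 does not ask for that, and it would discard samples from a PK subset whose size is not stated.
2. **SAP 13:** declare that the time-to-steady-state assessment is dropped and why. If the sponsor decides not to restore the time-from-last-dose summary, declare that too.
3. **Protocol synopsis:** align the PK wording with 10.4.5.

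The cost is some wording, one table and one plot, all from dose and sample times already recorded under protocol 6.5. The downside is small cells, which is a reason to use few bands and to rely mainly on the plot.
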